## **15. Withdrawal of Subjects**

Any participant may withdraw from the study at any time without penalty and will continue to receive the clinical standard of care. A subject may be withdrawn from the study without her consent at the discretion of the physician and study staff if they believe she no longer meets study inclusion criteria or if she meets exclusion criteria, or if they believe that it is not in her best interest to continue study participation. Investigators may withdraw a subject if the subject is not following the study protocol. If a woman is withdrawn from the study either at her own discretion or that of the research staff, she may continue with conservative or surgical management of her SUI in the usual fashion.

To minimize withdrawal from the study, patients will be randomized just after deciding on non-surgical management and signing consent. According to the 2010 CONSORT guidelines, we will analyze all participants assessed for eligibility within the study. We will document reasons for withdrawal from the study including failure to meet eligibility criteria or participant declining enrollment into the study. We will report eligibility criteria not met or reasons for declining participation in the study. The withdrawal procedure is clearly documented in the study consent.

## **16. Data Management/Confidentiality**

Randomization assignment will be generated by computer based randomization table and assigned by a research coordinator not otherwise involved in the study. Assignments will be kept in sealed opaque envelopes numbered sequentially, and on the day of the patient's clinic visit a research coordinator will open the next envelope in the sequence. This de-identified study subject number will then be assigned to the patient. All data collection sheets and questionnaires will contain the subject number and day of the clinic visit. No other patient identifiers will be collected on study forms. PHI including patient name, date of birth, phone

PROTOCOL TITLE: *SQEASI: Systematized Quality Exercise Alternatives for Stress Incontinence*

number, and medical record number will be collected to track appointments and kept separate from participant study data in a locked, secured office.

The data collection, HIPAA and consent forms will be maintained in a locked file cabinet in the Eubank research office. A separate folder will be designated for each participant. The offices have the additional security of being badge-access only for UNMH OBGYN department employees. A key matching study number to subject's name will be stored on a password protected computer on a secure UNM OBGYN department server. .

The only PHI collected will be patient name, date of birth, and telephone number for site use only and to ensure patient follow up. This will not be entered into the database, but it will be kept with the other identifying information.

The data does not include sensitive information or information requiring additional protection.

All data will be kept in a locked file cabinet in the research administrative area. In order to further ensure patient confidentiality, the identifying information will be kept separately from the numbered study files in a locked cabinet.

Electronic data entry will be performed in the OBGYN administrative offices, using the de-identified subject study number. The electronic data will be encrypted, password protected, and stored on the secure UNM OBGYN department server. This server's electronic security is monitored / maintained by the Health Sciences Library and Informatics Center (HSLIC). A REDCAP database will be created to collect, store and manage the data. REDCAP databases are reposed securely and all data entered is deidentified. The REDCAP database is only accessible using a individual unique login and password and access is only provided to co-investigators. Access is restricted to co-investigators and will be protected using the unique REDCAP login and password provided to each co-investigator.

Access to the files and REDCAP will be restricted to research personnel and Investigators and will be locked or protected using the unique REDCAP login and password provided to each co-investigator. The data will be stored for 5 years after completion of analysis and then will be destroyed.

A Certificate of Confidentiality will not be used to protect data from forced release. No identifying or study related data will be transported to outside locations. There will be no audio or video recordings or photographs taken.

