**PROTOCOL TITLE: SQEASI: Systematized Quality Exercise Alternatives for Stress Incontinence**

will be recruited in the UNM Eubank and SRMC clinic. All patients will have a complete history and physical taken. They will undergo a pelvic exam where they will be instructed on how to perform a pelvic floor contraction correctly and a cough stress test will be performed as part of the standard of care. After recruitment, they will undergo the consent process, and fill out initial questionnaires in the outpatient offices. Patients randomized to the biofeedback group will be given their devices in clinic and research staff will assist in setting up the device and downloading the phone app. The patients randomized to physical therapy will have their PFPT at the UNM Eubank clinic. To standardize therapy for these women all of our pelvic floor physical therapists will provide women with the same set of exercises and standard schedule of one initial visit and 3 follow up appointments. All other follow-up will be performed in the above-mentioned outpatient clinics.

There are no laboratory tests in this trial other than what would routinely be collected for the workup of SUI, nor is there involvement of any community advisory board. We do not perform urodynamic studies prior to managing patients with SUI with conservative therapy, so this study will not be performed. Also, there will not be any research conducted outside of the UNM HSC and its affiliates.

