## **12. Study Procedures**

This non-blinded, non-inferiority randomized controlled trial will be conducted at the UNM Eubank Clinic and SRMC Urogynecology clinic. Each site will recruit participants and we will plan to obtain up to 75 between the two sites. Collaborating investigators will be members of the Urogynecology Division at UNM HSC.

The primary aim of our study is to determine if quality of life is improved with use PFPT versus home biofeedback therapy alone in women with SUI. The target population will be patients with SUI who are seeking care. The current recommendation is to advise patient undergo conservative management with PFPT, try an incontinence pessary, or request the patient perform exercises at home. For all patients who present for treatment of SUI, we will take a thorough history and physical (including a POP-Q pelvic examination), score vaginal muscle strength based on Modified Oxford Grading Scale, perform a cough stress test to assess for SUI, and counsel the patient on all of her options including medical and surgical interventions.

If the patient is interested in conservative management and fulfills study inclusion criteria, we will then offer her the choice of volunteering for the study. All women will give written consent prior to their enrollment at this time and fill out questionnaires in the clinic. Research staff and clinicians will obtain consent and administer study questionnaires. After enrollment, participants will fill out baseline surveys, including the International Consultation on Incontinence Questionnaire- Short form (ICIQ-SF), Incontinence Severity Index (ISI), European Quality of Life-5 dimensions (EQ-5D), Overactive Bladder Questionnaire short form (OAB-q SF) Pelvic Organ Prolapse Incontinence Sexual Questionnaire (PISQ-12), and Female Sexual Function Index (FSFI). Data collected in addition to the above outcome measures includes patient demographics, medical/surgical History, and contact information, which are attached as supporting documents. This information will be collected from the patient on the day of enrollment and we will review the patient's medical record if information is missing or unclear.

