Randomization assignment will be generated by computer based randomization table and assigned by a research coordinator not otherwise involved in the study. Assignments will be kept in sealed opaque envelopes numbered sequentially. On the day of the patient's clinic visit, after signing consent and deciding to participate, the research coordinator will bring the next envelope in the sequence will be opened, randomizing the patient to PFPT or home biofeedback. The therapy allocation will then be carried out.

The biofeedback group will be given a PeriCoach® biofeedback device, which has a Bluetooth connection to a smartphone, free of charge. The smartphone application will be uploaded during the visit and linked to the device to ensure the patient understands how to

PROTOCOL TITLE: *SQEASI: Systematized Quality Exercise Alternatives for Stress Incontinence*

install the program. An information sheet with recommendation for exercise frequency will be given at the time of enrollment to provide recommendations for use. All participants will start as a beginner in the program and works up to a maintenance level. At the end we expect they will be doing 15 exercises, 3 times per day per manufacturer's instructions. 2 weeks following enrollment, these patients will be called to ensure they understand how device functions and are not having technical difficulties. When the patient returns for the 3 month follow up the smartphone app will be reviewed as the app records how often the patient performs the exercises. If that is not available, we will have the patient self-report her exercise frequency.

For patients randomized to physical therapy, PFPT will be scheduled for 4 sessions over 3 months, as is common practice for patients with SUI. These patients will receive instructions on how to engage their core, contract their vaginal muscles, as well as recommendations for home exercises to be performed for 3 sessions per day. The first session will be to establish the patient's baseline abilities with follow up sessions to reinforce instructions, performance of exercises and to ensure the patient is improving. Patient compliance of attending PT sessions will be recorded, as will the amount each patient spends in co-pays per session. After 3 months, regardless of the number of appointments the patient has attended, she will return for a follow up visit to assess how well she is doing.

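### The plan does not secure that the self-reported baseline ICIQ-SF is completed before the allocation envelope is opened

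*Combined protocol and SAP*

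**What the plan says.** Five sections of the combined protocol and SAP bear on the order of events at the enrolment visit.

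- **Section 8 (Research Setting)** puts the questionnaires after consent: "After recruitment, they will undergo the consent process, and fill out initial questionnaires in the outpatient offices". It then turns to handing out devices. It does not mention the envelope.
- **Section 12 (Study Procedures)** says "After enrollment, participants will fill out baseline surveys", and the ICIQ-SF is first on its list. A later paragraph describes allocation: "after signing consent and deciding to participate, the research coordinator will bring the next envelope in the sequence will be opened". The stated trigger is consent and the decision to take part.
- **Section 15 (Withdrawal of Subjects)** says that "patients will be randomized just after deciding on non-surgical management and signing consent". Questionnaires are not mentioned.
- **Section 16 (Data Management/Confidentiality)** says that "a research coordinator will open the next envelope in the sequence. This de-identified study subject number will then be assigned to the patient". It adds "All data collection sheets and questionnaires will contain the subject number and day of the clinic visit" and "No other patient identifiers will be collected on study forms". No exception is made for baseline forms.
- **Section 3 (Study Design)** confirms that the trial is unmasked and that each woman is told her arm.

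The primary endpoint (Section 7) is the 3-month change in ICIQ-SF. Section 13 compares continuous outcomes with t-tests.

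**The concern.** The ICIQ-SF is self-reported. A woman who has just learned whether she will receive a free device or attend four physical therapy visits may rate her symptoms differently from one who does not yet know. If the baseline is taken at that point, it is no longer a pre-randomization measurement, and randomization does not protect it from differing systematically between arms.

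The baseline is half of every change score. In an unadjusted comparison of change, a shift in mean baseline between arms passes in full into the estimated treatment difference. A non-inferiority conclusion rests on where that difference lies relative to a fixed 4-point margin, so a shift well below the margin still matters.

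The analysis cannot repair this afterwards. Section 13 provides a multivariate analysis if baseline differences appear, but a post-allocation baseline gives no means of separating chance imbalance from imbalance caused by knowing the arm.

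**Working it through.** **Order of events, reading the sections together**

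1. Trigger for allocation: Sections 12 and 15 both name consent. Neither requires completed questionnaires first.
2. Timing of baseline forms: Section 8 puts them after consent, Section 12 after enrolment. Neither places them relative to the envelope.
3. Identifier: Section 16 issues the number once the envelope is opened, requires it on every form and allows no other identifier.
4. Result: staff can follow every sentence and still open the envelope, write the number on blank forms and hand these to a woman who knows her arm. They can equally collect the forms first and number them afterwards. The documents allow both orders.

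**Illustration of what is at stake**

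Inputs from Sections 5 and 13: margin 4 points, 21 per group, 80% power, alpha 0.05 with sidedness not stated. No SD is given, so it is back-solved. Assumptions: a t-based non-inferiority test on change scores, equal SD in both arms, a true difference of zero for power, and an arm-related baseline shift of b points. The size of b is assumed.

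- Degrees of freedom: 2 × 21 − 2 = 40.
- Standard error: SE = SD × √(2/21).
- SD: the value at which a noncentral t with noncentrality 4/SE exceeds the critical value with probability 0.80.
- False non-inferiority, true difference at the margin and shift favouring biofeedback: noncentrality b/SE.
- Power, true difference zero and shift against biofeedback: noncentrality (4 − b)/SE.

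| | One-sided 0.05 | One-sided 0.025 |
|---|---|---|
| Critical t, 40 df | 1.684 | 2.021 |
| Back-solved SD | 5.12 | 4.51 |
| SE | 5.12 × 0.3086 = 1.580 | 4.51 × 0.3086 = 1.392 |
| False non-inferiority, b = 0 | 5% | 2.5% |
| b = 0.5 | 9% | 5% |
| b = 1 | noncentrality 1/1.580 = 0.633: 15% | 1/1.392 = 0.718: 10% |
| b = 2 | 34% | 29% |
| Power, no shift | 80% | 80% |
| Power, 1 point against biofeedback | noncentrality 3/1.580 = 1.899: 59% | 3/1.392 = 2.155: 56% |

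A normal approximation agrees closely. At SD 5.15 and one-sided 0.05, a 1-point shift gives 15.5% false non-inferiority, or power of about 60%. At SD 4.57 and one-sided 0.025, it gives 10.6%, or about 57%.

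**The case against.** A reader might infer that the plan actually schedules the baseline forms after allocation. The documents do not support that.

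- Sections 8 and 12 both narrate questionnaires first and allocation later, and Section 12 pairs consent and questionnaires in one sentence. This suggests that baseline first was intended.
- Enrolment is not randomization. Section 12 links it to consent, and Section 23 uses the word for the initial visit. Baseline surveys after enrolment are therefore not necessarily surveys after allocation.
- The numbering rule says what a form must carry, not when it is filled in. A number can be added to a completed form. The envelopes are numbered in sequence, so the number may even be known before one is opened.
- The Section 15 sentence explains how withdrawals are kept down. It does not exclude questionnaires at the same visit.

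A reader might also infer that any bias would favour biofeedback. The documents do not support that either. Section 1 expects women to prefer home therapy. If pleased women report milder symptoms at baseline, the biofeedback arm has less improvement to show, and the bias works against non-inferiority.

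Finally, a shift passes in full only into an unadjusted comparison of change. Adjustment for baseline would pass on part of it, roughly the baseline slope times the shift. That would reduce the bias without removing it, and Section 13 makes the adjustment conditional.

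All of this stands, and it limits the point to an order left unsecured. It does not remove the point: narrative order is not a rule, and the rules that are stated (envelope after consent, number from the envelope, number on every form) make the unwanted order possible and convenient.

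**Conclusion.** The order of baseline questionnaires and allocation is not secured, and the self-reported baseline of the primary endpoint can be collected after the woman knows her arm. This is a gap between Sections 8 and 12 on one side and Sections 15 and 16 on the other. It is not a stated decision to randomize first.

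The possible bias has no established direction or size. For an assumed shift of 1 point, a quarter of the margin, the cost is either a false non-inferiority rate about three times nominal (15% against 5%) or four times nominal (10% against 2.5%), or a loss of 21 to 24 percentage points of power (80% to 59% or 56%). These figures depend on the back-solved SD, the two readings of alpha, 21 analysed per arm and an unadjusted change-score test. They show sensitivity and do not predict what will happen. Because prevention is nearly free and repair at analysis is not possible, the wording should be changed.

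**What to change.** State one order, in the same words, in Sections 12, 15 and 16:

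1. Written consent.
2. Study number assigned from a consent log, independent of the allocation envelope.
3. All baseline questionnaires completed and collected under that number.
4. Only then is the next envelope opened and the woman told her arm.

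In Section 16, replace the sentence that issues the number when the envelope is opened. In Section 15, make randomization follow collection of the baseline forms at the same visit, which keeps the aim of limiting withdrawals. The Oxford grade needs no change, because Section 12 already scores it at the work-up, before the study is offered.

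The cost is a few sentences and a consent log. The visit, staff, forms and sample size stay the same.

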## **17. Data and Specimen Banking**

As stated above, the data collection, HIPAA and consent forms will be maintained in a locked file cabinet in the Eubank research area. A separate folder will be designated for each participant. A key matching study number to subject's name will be stored on a password protected computer on a secure UNM OBGYN department server.. In order to further ensure patient confidentiality, the identifying information will be kept separately from the numbered study files in a locked cabinet. The data will be maintained for 5 years after completion of the study and then destroyed.

No specimens will be archived for future use.

## **18. Risks to Subjects**

Risks of enrollment in the study include loss of confidentiality. We will take every measure to try to ensure the security and confidentiality of participants. Participants will be recruited in a private room and will have ample time to consider whether they want to participate in the study. Also, locked filing cabinets will be used to protect patient consent information and collected data. The link identifying patients and their study numbers will be also stored on a password protected computer on a secure UNM OBGYN department server.

Additionally, each patient who will be offered enrollment will already have agreed to non-surgical treatment of her SUI. There are minimal risks with either study arm of this RCT. PFPT therapy could cause sore muscles or vaginal spotting after treatment, but these are rare. Emotional discomfort due to the intimate nature of this therapy is also possible. Biofeedback devices carry the same risks. Both treatment randomizations in this study are well established as options for SUI with an excellent safety profile.

Pregnant women will not be included in the study, so there is no risk to embryos/fetuses. If there is concern for pregnancy, we will test the participant on the day of enrollment. If they are pregnant, the patient meets exclusion criteria and will be ineligible to participate.

There are no risks to those who are not subjects.

## **19. Potential Benefits to Subjects**

The patients enrolled are already opting for non-surgical treatment of their SUI. Participation in this study may help to improve an individual participant's condition, but it is also possible that the condition may not improve. There is no guarantee that any individual will

**PROTOCOL TITLE: SQEASI: Systematized Quality Exercise Alternatives for Stress Incontinence**

personally benefit by participating in this research study. Women who are randomized to at home biofeedback will potentially get benefit from having a personal device they can keep. Participation in this study may provide information that may help other people who have a similar medical problem in the future. The literature supports improvement of QOL with improved SUI. PFPT and biofeedback have both been successfully used to treat SUI in the past.

## **20. Recruitment Methods**

We will recruit women from our urogynecology clinical practice and we do plan to advertise for this study, including on social media.

The urogynecology clinics at UNM Eubank, and SRMC have a large referral population of patients with pelvic floor conditions and SUI. Subjects will be identified in the clinics at UNM Eubank clinic, and SRMC by investigators. The patients will be counseled about possible treatment options for SUI including non-surgical and surgical techniques. If the patients have SUI or mixed urinary incontinence with >50% stress, they will be introduced to the study and provided with written information that may help them decide if participation in the study is right for them. Subjects are encouraged to consult with family, friends, and primary health care providers, as well as communicate any questions they may have before beginning the written consent process. We will request a waiver of HIPAA authorization for recruitment purposes.

If a woman declines to participate or is withdrawn from the study either by her desire or that of the research staff, she will be offered the same treatment options. Her follow up appointments will be the same regardless of participation in the study.

Potential participants may also self-identify through a recruitment material flyer that will be placed in Eubank clinic restrooms, waiting area and in the OB/GYN department at UNM. The proposed recruitment flyer is uploaded in the supplemental materials section. We will also plan to recruit using social media. The proposed wording is included in the website advertisement in the supplemental materials section

## **21. Provisions to Protect the Privacy Interests of Subjects**

Privacy concerns are taken into account with every patient seen at the UNM and SRMC clinics. Participants approached and/or interviewed in the clinic setting will be in private offices or examination rooms in the UNM Eubank, or SRMC clinics, where all staff, including research staff, are well-versed in sensitive health care discussions and procedures. Telephone interviews for recruitment and study data gathering are conducted in the research staff area or private physician offices, where all staff have received CITI Training. The office area designated for the entire urogynecology research staff is isolated from the clinical administrative staff area,

PROTOCOL TITLE: *SQEASI: Systematized Quality Exercise Alternatives for Stress Incontinence*

providing protection for participants and potential participants during screening, recruitment, study-designated calls, and data entry. All study sheets used to collect patient information will be de-identified.

At all times throughout the clinical investigation, confidentiality will be observed by all parties involved. All data will be secured against unauthorized access. Privacy and confidentiality of information about each subject will be preserved in study reports and in any publication. Each subject participating in this study will be assigned a unique identifier. An IRB-approved HIPAA authorization is required to be signed. All documents containing personal health information (screening logs, consent documents, data forms) are maintained in locked file cabinets with access available only to research staff and investigators. Data is entered into a password protected system. No individual identifiers are entered into the system. The sole link with personal information is maintained by the research team on a password protected computer on a secure UNM OBGYN department server with access limited to authorized research staff and investigators. This information is only to be used at the study center.

